7.2 Types of study

Observational Cross Sectional Study

7.3 Study population/Sampling frame

A sample of adult patients (age ≥ 18 years) who have either come to OPD for follow-up or have been readmitted for having cardiac complications months after surviving ACS (including STEMI, NSTEMI, and unstable angina) in Manmohan Cardiothoracic Vascular and Transplant Centre, Nepal will be selected via **convenience sampling**. The total population under study is around 1000.

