In summary, this study is essential for understanding why patients in Nepal fail to adhere to life-saving medications post-ACS and what can be done to mitigate this problem, ultimately improving patient care and reducing the burden on the healthcare system.

5. Objectives

a. General objectives:

To assess the level of adherence to prescribed secondary prevention medications and identify the factors influencing adherence among patients with Acute Coronary Syndrome (ACS) in Nepal.

b. Specific objectives:

- **To assess the level of adherence to secondary prevention medications (SPMs) among patients discharged after an Acute Coronary Syndrome (ACS) event, including antiplatelets, statins, beta-blockers, and ACE inhibitors/ARBs.**
- **To explore the influence of patient demographic factors** (such as age, gender, education level, occupation, and place of residence) and clinical characteristics (type of ACS, comorbidities) on medication adherence.
- **To identify patient-reported barriers to medication adherence**, including concerns about medication side effects, pill burden, practical issues with medication administration, and difficulties in integrating medications into daily routines.
- **To evaluate the relationship between medication adherence and clinical outcomes**, such as recurrent cardiac events, rehospitalization.

6. Research questions/hypothesis

- What is the level of adherence to secondary prevention medications among Acute Coronary Syndrome (ACS) patients in Nepal, and what demographic, clinical, and patient-reported factors influence this adherence and its associated clinical outcomes?

7. Research design and Methodology

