7.1. Research method

Quantitative Survey: The adherence to secondary prevention medications among re-hospitalized patients after cardiac complications following Acute Coronary Syndrome (ACS) will be evaluated using a structured questionnaire. This survey will assess patient demographics, socioeconomic status, and barriers to adherence such as medication cost, side effects, and treatment complexity. Administered either in person or via an online platform, the survey will collect key data on adherence patterns and influencing factors in high-risk patients. This method aims to ensure efficient data collection while maintaining confidentiality and ease of access for participants.

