7.5 Sampling method

In our research study, we will employ convenience sampling. Convenience sampling is a non-probability method where units are selected for inclusion in the sample because they are the easiest for the researcher to access. The target population consists of adult patients (age ≥ 18 years) who have either come to OPD for follow-up or have been readmitted in hospital for having cardiac complications months after surviving ACS (including STEMI, NSTEMI, and unstable angina). Rather than applying specific

stratification based on cancer type, we will approach patients who are readily available within the hospital setting. We will use the MYMEDS questionnaire. The researcher will personally ask all the questions and fill out the questionnaire for each eligible patient. To assess the socioeconomic status of participants, we will utilize the Modified Kuppuswamy's Socioeconomic Status Scale, adapted to the context of Nepal (18). Alongside demographic information such as gender, age at diagnosis, and marital status, we will collect data on education level, occupation, and family income, as per the scale's criteria(18).

Once we collect the responses, we will use MS Excel for data entry and analyze the data using SPSS version 29.

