7.10 Tools and techniques for data collection

- Tools:

Questionnaire

The questionnaire is composed of six simple-to-complete sections.

Section 1:

- Patients provide essential contextual information about the medicines they are taking, when they are administered each day, and their understanding of why they are taking them.
- This helps clinicians compare a patient's actual medication usage with documented clinical records and uncover any medication changes since discharge.

Subsequent sections (Section 2-6):

- These sections use Likert scales instead of binary yes/no responses, which improves the quality of information gathered.
- For example, it allows the assessment of the frequency of non-adherence behaviors rather than just detecting non-adherence.

Section 2:

- Explores overall understanding and satisfaction with medicines.
- Patients respond to four statements regarding their understanding of why their medicines were prescribed and how well they think they are working, using a four-point Likert scale (strongly agree, agree, disagree, strongly disagree).

Sections 3–5:

- Assess specific modifiable barriers to adherence, using the same four-point Likert scale as section 2.
- A free-text box allows patients to specify which medicines their concerns involve.

Section 3:

- Explores three areas of anxiety about medicines (e.g., concerns about medicines causing more harm than good or feeling there are too many medicines).

Section 4:

- Examines four practical concerns associated with medicine-taking (e.g., difficulties with swallowing pills or obtaining repeat prescriptions).

Section 5:

- Assesses three issues related to fitting medicines into the patient's daily routine (e.g., forgetfulness or inconvenience).
- These issues are linked to non-adherence and can potentially be addressed in clinical practice.

Section 6:

- Focuses on adherence to each individual secondary prevention medication (SPM) over the past month.
- It uses a modified version of the SQ tool and a five-point Likert scale.
- Patients are considered non-adherent if they select any answer other than 'all of the time' for any SPM.

[figure not shown]
Technique:

- A relevant questionnaire will be developed and distributed to our research team. They will visit cardiology outpatient department (OPD) as well as in the cardiology ward in Manmohan

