	c. I have difficulties or problems getting my repeat prescriptions and would like help ordering them from my GP or pharmacy.				
	d. I have difficulties or problems reading the label on the medicines bottle or box and would like a solution or alternative.				

Section 5: Fitting medicines into daily routine	a. I sometimes forget to take my heart medicines.				
	b. I am finding it difficult to fit one or more of my heart medicines into my daily routine.				
	c. I feel inconvenienced/bothered about sticking to all my heart medicines.				

Section 6: Adherence to Individual SPMs

For each of your prescribed medicines (SPMs), please indicate how often you have taken them as prescribed in the PAST MONTH:

Medication	All of the Time	Nearly All of the Time	Most of the Time	About Half the Time	Less than Half the Time
Aspirin					
ACE Inhibitor (e.g. Ramipril, Lisinopril,)					
Beta Blocker (e.g. Acebutalol)					
Medication 4 Statin (e.g. Simvastatin)					
ARIIA (e.g. Candesartan)					

Section 4: Clinical Outcomes

1. **Have you experienced any of the following since discharge?** (Check all that apply)
 - Recurrent chest pain
 - Rehospitalization for cardiac issues
 - Stroke
 - Heart failure symptoms
 - No major events
2. **Follow-up with healthcare provider since discharge:**
 - Yes
 - No
 - If Yes, how many visits: _____

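### Readmission is both a way into the sample and an objective 4 outcome, so any pooled rehospitalization rate, risk ratio or risk difference by adherence would depend on how many ward patients are recruited

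*Combined protocol and SAP*

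**What the plan says.** **Entry.** Section 7.3 defines the sample as adults "who have either come to OPD for follow-up or have been readmitted for having cardiac complications months after surviving ACS". Section 7.5 repeats both routes and adds that "we will approach patients who are readily available within the hospital setting". Section 7.10 sends staff to the cardiology outpatient department and the cardiology ward. No quota, ratio, consecutive-patient rule or weighting by setting is given. Section 7.3 also says "The total population under study is around 1000", with no split by readmission status.

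**Outcome.** The fourth specific objective (Section 5b) relates adherence to clinical outcomes "such as recurrent cardiac events, rehospitalization". In Annex 1, Section 4 (Clinical Outcomes), the item begins "Have you experienced any of the following since discharge" and one tick-box is "Rehospitalization for cardiac issues". The current admission is not excluded.

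**Exposure.** Section 6 of the questionnaire covers adherence in the month before interview only.

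**Analysis.** Section 8 contains only template prompts. Section 7.8 lists adherence as the dependent variable and does not list rehospitalization at all. No effect measure is named for objective 4.

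**Inconsistent population.** Section 7.1 and the first expected outcome in Section 13 describe re-hospitalized patients only.

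**The concern.** A patient approached on the ward because of a cardiac readmission will tick the rehospitalization box by definition. Many OPD patients will not. The proportion of the sample with the outcome is therefore set largely by how many ward patients the staff happen to approach. This is sampling on the outcome, although Section 7.2 labels the study cross-sectional.

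The natural table for objective 4 would show the percentage rehospitalized among adherent and non-adherent patients. Those percentages, and any risk ratio or risk difference built from them, would describe no population, and they would change if the team spent more days on the ward. Recording event dates would not cure this, because the problem lies in who is selected. The source population is not split by readmission status, so the documents give no basis for reweighting afterwards.

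**Working it through.** The plan states no figure for objective 4. Two of its figures are used here.

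- Total sample: 1.96² × 0.925 × 0.075 / 0.05² = 106.6 (the plan prints 106.39 and rounds to 106); 106 × 1.10 = 116.6, so N = 117 is reproduced.
- Non-adherence: 1 − 0.925 = 7.5%. Section 7.6 takes the 92.5% from another centre and another tool, so it is only a placeholder here.

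**Assumed, not in the documents:** readmission risk of 20% if non-adherent and 10% if adherent (risk ratio 2.0, difference 10 points, odds ratio 2.25).

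**Step 1: source population.**
- Readmitted: non-adherent 0.075 × 0.20 = 0.0150; adherent 0.925 × 0.10 = 0.0925; total 0.1075.
- Not readmitted: non-adherent 0.0600; adherent 0.8325; total 0.8925.
- Non-adherence among readmitted patients: 0.0150/0.1075 = 14.0%. Among the others: 0.0600/0.8925 = 6.7%.

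**Step 2: let a share f of the sample be readmitted patients.** The apparent risk in the non-adherent is 0.1395f / [0.1395f + 0.0672(1 − f)]. For the adherent, use 0.8605 and 0.9328.

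| f | Non-adherent | Adherent | Risk ratio | Difference | Odds ratio |
|---|---|---|---|---|---|
| 25% | 40.9% | 23.5% | 1.74 | 17 points | 2.25 |
| 50% | 67.5% | 48.0% | 1.41 | 20 points | 2.25 |
| 75% | 86.2% | 73.5% | 1.17 | 13 points | 2.25 |

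The risk ratio reads 2.0 only if f equals the source share of 10.75%. The odds ratio and the two proportions in Step 1 do not change with f.

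**Step 3: other assumptions.** With risks of 30% and 15% (odds ratio 2.43), adherence 92.5% and no past readmissions in OPD, moving from 12 to 105 ward patients out of 117 takes the rehospitalization percentage from 10.3% to 89.7% and the risk ratio from 2.14 to 1.07. At 70% adherence the risk ratio runs from 2.19 to 1.09, and at 50% from 2.22 to 1.10. If OPD patients carry the source share of past readmissions (adherence 92.5%), it runs from 1.82 to 1.06.

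**Step 4: who counts as a case.** Return to the 20%/10% risks. Suppose 15% of OPD patients had an earlier readmission and their current adherence now matches that of never-readmitted patients (both assumed). Counting them as cases at a 50% ward share gives:
- non-adherent cases 0.5 × 0.1395 + 0.5 × 0.15 × 0.0672 = 0.0748;
- adherent cases 0.5 × 0.8605 + 0.5 × 0.15 × 0.9328 = 0.5002;
- odds ratio (0.0748/0.5002) / (0.0600/0.8325) = 2.08, not 2.25.

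At ward shares of 10%, 25% and 75% it is 1.51, 1.84 and 2.19. The odds ratio then depends on the mix again.

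**Step 5: precision at a 50% mix, N = 117 (58.5 per group).** Expected counts are 8.16 and 50.34 among cases, 3.93 and 54.57 among controls. The standard error of the log odds ratio is √(1/8.16 + 1/50.34 + 1/3.93 + 1/54.57) = 0.644. The approximate 95% CI is 2.25 × exp(±1.96 × 0.644) = 0.64 to 7.95.

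**The case against.** The strongest reply is that no affected estimate is planned. A reader might infer that the protocol intends to compare rehospitalization risk between adherent and non-adherent patients. The documents do not say so. Objective 4 speaks only of a relationship, the project summary of correlations, and Section 7.8 makes adherence the dependent variable. Section 9 discusses comparing adherence between OPD and re-hospitalized patients, which is the direction that survives this kind of sampling. This stands: the point is that the plan leaves the wrong direction open, not that it chose it.

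A reader might also infer that the odds ratio is the only acceptable measure and is safe whatever the mix. Neither follows. Non-adherence by readmission status is equally unaffected by the mix and simpler for a descriptive study. Step 4 shows that the odds ratio loses the property once OPD patients with earlier readmissions are pooled with ward cases, because their past-month adherence is measured after the event. Convenience recruitment may also select on adherence within a setting, for example if OPD attenders are the more adherent patients.

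Sections 9 and 10 do acknowledge differences between the two settings, survivor bias, confounding and the cross-sectional limit. None of these says that readmission is itself an outcome, so they do not cover the point.

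Finally, the magnitudes are illustrative. The 7.5% comes from a different instrument, while Section 7.10 counts anything short of full adherence to any one medicine as non-adherent. The dependence on ward share does not rest on those values.

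**Conclusion.** The point holds as limited here. The stated recruitment routes and outcome item together mean that any pooled rehospitalization rate, risk ratio or risk difference by adherence would vary with the number of ward patients, and no section of the plan rules such a figure out. In the main illustration a true risk ratio of 2.0 reads anywhere from 1.74 to 1.17 as the readmitted share goes from 25% to 75%. The size depends on the assumed risks; the dependence itself follows from the design whenever adherence and readmission are associated.

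Only objective 4 is at issue. Comparing non-adherence by readmission status is usable if recruitment within each setting does not depend on adherence and if earlier OPD readmissions are kept apart. It will be imprecise: 7.5% of 117 is about 9 non-adherent patients. Even at the 50% mix, where the assumed enrichment of cases raises that to about 12 (8.2 + 3.9), the interval runs from 0.64 to 7.95.

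If Sections 7.1 and 13 were followed literally, there would be no OPD patients and no comparison at all.

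**What to change.** 1. Reconcile Sections 7.1 and 13 with Sections 7.3 to 7.5 on whether OPD patients are included. Objective 4 needs them.
2. Add a recruitment-setting tick-box (OPD or ward) to the Annex 1 proforma, which has none, and report the numbers by setting. Together with the existing rehospitalization item, this separates the three groups below.
3. In Section 8, specify for objective 4 a comparison of past-month non-adherence between patients recruited during a readmission (cases) and OPD patients with no readmission since discharge (controls), as proportions, an odds ratio with 95% CI, or both.
4. Report OPD patients with an earlier readmission separately.
5. State that no pooled rehospitalization rate, risk ratio or risk difference will be reported.
6. Add two limitations to Section 10: the comparison assumes that recruitment within each setting is unrelated to adherence, and it will be imprecise.

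The cost is one form field and some analysis wording. The report cannot then give a rehospitalization rate, but this sample could not support one anyway.

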7.4 Study site and its justification

This descriptive cross-sectional study will be conducted at Manmohan Cardiothoracic Vascular and Transplant Centre, a premier tertiary care institution in Nepal, specializing in cardiovascular care. As one of the nation's leading centres for heart disease management, it offers advanced diagnostic, therapeutic, and surgical services to patients with a wide spectrum of cardiovascular conditions, including Acute Coronary Syndrome (ACS). The centre's reputation for excellence in cardiology and its strategic location make it an ideal setting for research into adherence to secondary prevention medications after ACS.

The patient population at this centre is diverse, including individuals from both urban and rural areas of Nepal, which provides a comprehensive understanding of medication adherence patterns across various demographic and socioeconomic groups. The centre regularly follows up with ACS survivors, both through outpatient visits and during readmissions for cardiac complications. This makes it a prime location to study patients who have either come for follow-up visits or been readmitted within 12 months of their initial ACS event, including STEMI, NSTEMI, and unstable angina.

By focusing on this centre, the research will leverage the expertise of its specialized staff and access to detailed patient records, providing valuable insights into medication adherence in real-world clinical practice. These insights can then be used to inform targeted interventions to improve long-term outcomes for ACS survivors across Nepal.

7.5 Sampling method

In our research study, we will employ convenience sampling. Convenience sampling is a non-probability method where units are selected for inclusion in the sample because they are the easiest for the researcher to access. The target population consists of adult patients (age ≥ 18 years) who have either come to OPD for follow-up or have been readmitted in hospital for having cardiac complications months after surviving ACS (including STEMI, NSTEMI, and unstable angina). Rather than applying specific

stratification based on cancer type, we will approach patients who are readily available within the hospital setting. We will use the MYMEDS questionnaire. The researcher will personally ask all the questions and fill out the questionnaire for each eligible patient. To assess the socioeconomic status of participants, we will utilize the Modified Kuppuswamy's Socioeconomic Status Scale, adapted to the context of Nepal (18). Alongside demographic information such as gender, age at diagnosis, and marital status, we will collect data on education level, occupation, and family income, as per the scale's criteria(18).

Once we collect the responses, we will use MS Excel for data entry and analyze the data using SPSS version 29.

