7.6 Sample size

Based on the assumptions that the margin of error is 5%, the confidence level is 95%, the response distribution is 50%, and the prevalence of adherence to medication is 92.5%, the sample size for our study is 117. These assumptions are used to determine the sample size required to estimate a population parameter with a certain level of precision. The prevalence of adherence to medication (92.5%) was taken from a study conducted at Shahid Gangalal National Heart Centre in 2018, which reported that 92.5% of respondents were highly adherent to medication, as measured by the Morisky, Green, and Levine (MGL) scale 4-item questionnaire.

The sample size (n) is calculated according to Cochran's formula: $n = [z^2 * p * q / d^2]$

Where: z = 1.96 for a confidence level (α) of 95%, p = proportion (expressed as a decimal), d = margin of error and adding a 10% non-response rate by using the following formula:

$z = 1.96$, $p = 0.925$, $d = 0.05$

$n = [1.96^2 * 0.924 * (1 - 0.817) / (0.05)^2] = 106.39$

$n \approx 106$

The sample size needed for the study is 106 participants. By adding 10% non-response, the sample size is increased to 117 participants.

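### Interviewers may take whichever eligible patients are easiest to reach, with no record of the rest, so the 5% margin in 7.6 covers random error only; a fixed approach rule and a screening log would reduce the risk of bias

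*Combined protocol and SAP*

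**What the plan says.** The project summary and sections 7.3 and 7.5 all specify convenience sampling of adults seen in the outpatient department (OPD) or readmitted after ACS. Section 7.5 is open about what this means: "Convenience sampling is a non-probability method", and "we will approach patients who are readily available within the hospital setting". Section 7.3 adds that "The total population under study is around 1000", without giving a period.

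Section 7.6 applies Cochran's single-proportion formula with a 5% margin, 95% confidence and assumed adherence of 92.5%. It describes its inputs as fixing "the sample size required to estimate a population parameter with a certain level of precision". The result is 106, raised to 117 for 10% non-response.

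Section 9 discusses selection bias as a difference between OPD and re-hospitalised patients, and adds survivor bias and self-report bias. Section 10 names the single centre and several other limits. Neither section mentions the interviewer's choice among eligible patients who are present, or says that the margin is nominal.

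**The concern.** The formula in 7.6 describes how far an estimate strays by chance when patients are drawn at random. Section 7.5 draws them by ease of access. Any link between being easy to reach and taking medicines as prescribed goes straight into the adherence level, which is the first specific objective, and a larger sample would not reduce it.

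The plan also collects little that would show the problem. It allows 10% for non-response but provides no count of patients eligible, approached or refusing, so that allowance cannot be checked. The proforma in the annex covers enrolled patients only. It asks about rehospitalisation since discharge but has no field for whether the patient was recruited in the OPD or on the ward. The mix of the two groups is therefore left to convenience, although section 9 itself expects them to differ. That mix also affects the objective relating adherence to rehospitalisation, because a patient recruited on the ward has been rehospitalised by definition.

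**Working it through.** **1. The plan's own figure.** Inputs from 7.6: z = 1.96, p = 0.925, d = 0.05.

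n = z² × p × (1 − p) / d² = 3.8416 × 0.925 × 0.075 / 0.0025 = 106.6.

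The plan gives 106.39, taken as 106. With non-response, 106 × 1.10 = 116.6, so 117. The figure reproduces from p = 0.925. (The printed substitution line uses 0.924 and 1 − 0.817, which would give 259.8. That is a separate matter, and the 106 does not come from it.)

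**2. What the margin covers.** Half-width = 1.96 × √(p(1 − p)/n). At p = 0.925 this is 5.0 points for n = 106 and 4.8 points for n = 117. The expression has no term for selection.

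**3. What selection bias would do to it.** The documents give no bias, so b is an assumption, shown over a range and in both directions. True adherence is taken as 92.5%, and the patients actually sampled have adherence 0.925 + b. With n = 106, an estimate lies within 5 points of 92.5% when 93 to 103 patients are adherent. The chance is the exact binomial sum over x = 93 to 103 of C(106, x)(0.925 + b)^x (0.075 − b)^(106 − x).

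| Assumed bias | Upward | Downward |
|---|---|---|
| none | 96% | 96% |
| 2 points | 93% | 87% |
| 3 points | 86% | 78% |
| 5 points | 50% | 54% |
| 10 points | not possible (above 100%) | 9% |

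With all 117 interviewed (x = 103 to 114) the picture is similar: 96% with no bias, 86–96% at 2 points, 75–90% at 3 points and 50–56% at 5 points.

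**4. What produces a bias of that size.** If a share a of eligible patients is easy to reach, a share s of the sample comes from them, and adherence differs by D between the two groups, the bias is (s − a) × D. As an illustration with assumed values, take a = 0.5 and D = 10 points. If the sample is drawn wholly from the easy-to-reach (s = 1), the bias is 0.5 × 10 = 5 points. If a quarter comes from the others (s = 0.75), it is 0.25 × 10 = 2.5 points. The sign depends on which group adheres better, and the documents do not say.

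**5. Whether a rule is already there.** Section 7.5 says the researcher completes the form for each eligible patient, and 7.10 says the team questions patients who meet the criteria. Both describe how the questionnaire is administered. Neither requires that every eligible patient be approached, and 7.5 states the opposite principle.

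**6. Workload.** 117 interviews over the six months in 7.9 (26 weeks) is 4.5 a week. Over December to June in the work plan (seven months, about 30.3 weeks) it is 3.9 a week. A different approach rule does not change these numbers.

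**The case against.** The best defence is that the plan is candid. It calls the sample non-probability, lists selection and survivor bias, and limits generalisability. The study is descriptive and at one centre, and the 5% and 95% appear as sample-size assumptions; no text promises to report the result with that precision. This is fair and keeps the point at the level of a recommended improvement. It does not answer the point, since the bias disclosed is between OPD and ward patients and the interviewer's choice within each is not mentioned.

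A second objection stands in full: consecutive sampling is also non-probability. A reader might infer that adopting it would make the ±5% valid. It would not. It takes away discretion among those present, but choice of days (unless fixed), attendance, refusal and survival still select. The margin also depends on p: at n = 117 the half-width is 7.25 points at p = 0.80 and 9.06 at p = 0.50.

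A reader might also infer that easy-to-reach patients are the better adherers, so that adherence will be overstated. The documents do not support a direction. Ward patients may be the easiest to reach of all, and section 9 says only that their adherence may differ.

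Nor do the documents show that the change is almost free. They give no clinic volume, interviewer numbers or visit schedule. The budget of Rs. 10000 covers printing and publication, and checking attenders against the criteria in 7.7 is real work.

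Finally, it would be too strong to say that nothing could reveal a bias. The proforma records age, gender, residence, ACS type and comorbidities, section 7.4 refers to detailed patient records, and section 12 promises to track recruitment. A comparison with centre records is possible. None is planned, however, and it would not measure adherence in the patients missed.

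**Conclusion.** The point holds as a recommended change to the design. The plan attaches a precision target that reflects chance alone to a sample chosen by ease of access, and it keeps no record by which the selection could be judged. If selection shifts adherence by 2 to 3 points, the chance of being within 5 points of the truth drops from about 96% to between 78% and 93%; at 5 points it is about one half. These figures rest on true adherence of 92.5%, n = 106 and biases that are assumed. They show how sensitive the margin is, and they are not an estimate of the bias in this study. The 5-point illustration in particular is one scenario among many. The conclusion does not need the bias to run in any particular direction.

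**What to change.** - In 7.3 and 7.5, replace convenience sampling by consecutive sampling on collection days fixed in advance. On each such day approach every eligible OPD attender and ward readmission, or every k-th on the list when there are too many to interview, until the target is met. Set k from actual clinic lists: the figure of 1000 in 7.3 has no period attached, so k cannot be derived from it.
- Keep a one-line log for each eligible patient: eligible, approached, refused, age, sex, and OPD or ward.
- Report the response rate, and report adherence separately for OPD and readmitted patients. This matters because recruiting to a single total can let the larger stream dominate.
- State in 7.6 and section 10 that the 5% margin is nominal and applies to attenders at this centre.

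**Cost.** The sample size (106, raised to 117) and the number of interviews do not change. The additions are eligibility screening and log-keeping on collection days, and less interviewer discretion. Because clinic volume and staffing are not given, this cost is judged small and has not been shown to be. If the sponsor keeps convenience sampling, the log, the separate reporting and the statement about the margin are still worth adding.
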